2.0 BACKGROUND

Study Disease

Hepatocellular carcinoma (HCC) is the most common primary liver cancer in the world and is one of the most rapidly growing causes of cancer-related death in the United States [1]. Multiple liver-directed treatment options are available to HCC patients, including liver transplantation, surgical resection,

radiofrequency ablation, catheter-based therapies, and radiation therapy (RT). HCC tumors often arise in the background of chronic liver disease such as alcohol, viral hepatitis, autoimmune hepatitis, or non-alcoholic fatty liver disease-related cirrhosis. Patients with cirrhosis commonly have impaired liver function, which plays a central role in determining which treatments patients can safely receive and how aggressive these treatments can be. Ultimately, tumor eradication with preservation of liver function is the desired treatment goal for HCC patients.

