3.0 STUDY OBJECTIVES

3.1 Primary Objectives

- a) Develop new quantitative metrics of baseline SC uptake on SPECT/CT imaging and correlate with clinical parameters of liver function and clinical outcomes in liver cancer patients receiving RT or surgery.
 - Hypothesis: Global metrics of baseline pre-treatment SC uptake on SPECT/CT imaging are more predictive for survival than conventional clinical measures of liver function and are associated with ICG clearance. For patients receiving surgery, the volume of the future liver remnant (FLR) as defined by SC SPECT/CT imaging (functional FLR) is more predictive for PHLF than CT-defined FLR volumes. Heterogeneity metrics of baseline SC uptake are associated with the severity of cirrhosis and prior liver-directed therapy; specifically, SC uptake within the liver is more heterogeneous in less compensated livers and in those that have received a higher number of liver-directed therapies.
- b) Correlate *post-treatment* changes in SC uptake on SPECT/CT imaging with changes clinical liver function.

Hypothesis: Changes in SC uptake between pre-RT and mid-RT/post-RT SPECT/CT scans are associated with changes in clinical liver function in response to RT and are predictive of liver toxicity at earlier time points compared to clinical assessments of liver function. SC uptake in the FLR (non-treated) is stable and preserved over time between pre-surgery and immediately post-surgery (3-5 days postoperative) scans.

Secondary Objectives

- a) Estimate the dose response relationship on multiple spatial scales (global liver, regional liver, liver image voxel) between radiation dose and changes in SC uptake, both acutely (mid-RT) and subacutely (1 month post-RT), using SC SPECT/CT imaging.
 - Hypothesis: Deficits in SC uptake due to absorbed dose is governed by a linear dose relationship. As the dose delivered to the region/voxel increases, the uptake in SC decreases in a linear fashion.
- b) Estimate the degree of radiation response in liver tissue with varying levels of function (i.e. compare radiation dose response of well compensated livers against less compensated livers).

This may establish a threshold of liver tissue that would be "safe" to treat without significantly affecting liver function.

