4.0 STUDY DESIGN

General Design

This is a pilot study of utilizing SPECT/CT imaging with 99m Tc-SC to accurately identify and quantitate functional liver tissue on serial imaging in patients receiving RT or surgery for liver cancer. The long-term goals are to use functional imaging to improve risk stratification for selecting which patients should undergo aggressive local treatments with RT or surgery and to aid in RT planning by preferentially sparing functional liver tissue, thereby leading to reduced liver toxicity. There will be two cohorts of patients: those receiving RT (Cohort A) and those undergoing surgery (Cohort B). A total of 60 patients will be enrolled (Cohort A, n = 40; Cohort B, n = 20).

All patients will have a total of 3 SPECT/CT imaging with ^{99m}Tc-SC. The first scan in both cohorts will be routine medical care (not experimental) and will take place prior to initiation of RT or surgery. Two follow up scans will be part of the protocol. In cohort A, the first follow up scan will occur at mid-RT, and the second one about 1 month post-RT (prior to any potential anatomical liver changes). In cohort B, the first follow-up scan will occur 3-5 days postoperatively (prior to any potential liver hypertrophy), and the second one about 1 month post-operatively (when liver hypertrophy is expected to occur).

Endpoints

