4.2.1 Primary Endpoints

a) Significant differences in Wilcoxon rank sum of ROC-optimized SC SPECT parameters will be tested between CTP classes. Spearman rank correlations between optimal SC SPECT parameters and clinical liver function parameters will be tabulated for the following categories: (1) composite liver function scoring systems (CTP score, ALBI grade), (2) individual quantitative liver function components (albumin, bilirubin, INR), and (3) individual qualitative clinical liver function components (encephalopathy, portal hypertension, ascites, and splenomegaly). Qualitative components will be treated as binary categorical variables (yes/no). Imaging and clinical parameters of liver function will be tested for association with overall survival. Continuous variables will be dichotomized above and below a threshold value that maximized accuracy of classification under ROC with balanced sensitivity and specificity. Univariate Cox proportional hazard regression will then be performed on all continuous and categorical variables. Statistically significant variables will serve as inputs into multivariate Cox proportional hazard regression. A stepwise backwards variable selection procedure will be followed to remove non-significant variables with high cross-correlation until the model log-likelihood is maximized.

Because radiomics generates feature sets of ~50 metrics, machine learning methods will be utilized to develop predictive models that are robust against overfitting, utilizing feature selection and classification/regression methods such as support vector machines, Bayesian analysis, and decision trees. These machine learning methods will be compared against standard statistical methods, such as ROC analysis and Kaplan-Meier estimation / Cox regression, for association to clinical liver function, prior liver-directed therapies, clinical outcomes (i.e. survival), and toxicity (i.e. CTP score progression).

b) The same set of statistical analysis will be performed for association of post-treatment changes in SC uptake on SPECT/CT imaging to clinical endpoints. Machine learning methods will test whether post-treatment changes in SC SPECT/CT provide independently predictive information after adjusting for baseline parameters.

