5.0 SUBJECT SELECTION

Inclusion Criteria

- 5.1.1 Patients with a diagnosis of HCC, intrahepatic cholangiocarcinoma, or metastatic liver cancer planned to receive definitive doses of radiation or surgical resection are eligible
- 5.1.2 Measurable hepatic disease and/or presence of vascular tumor thrombosis.
- 5.1.3 Diagnostic CT or MRI scan within 2 months of study entry.
- 5.1.4 There are no limits on prior therapy. Patients are allowed to have prior systemic therapy, radiation therapy, radiofrequency ablation, catheter-based therapies, and surgery. Patients are allowed to have concurrent chemotherapy with radiation treatment.
- 5.1.5 Patients >18 years old.
- 5.1.6 Ability to understand and the willingness to sign a written informed consent document.

Exclusion Criteria

- 5.1.7 Patients unable to tolerate a SPECT/CT ^{99m}Tc-SC scan.
- 5.1.8 Patients who are not planning to adhere to the required follow up schedule as outlined in this protocol.
- 5.1.9 Pregnant women.
- 5.1.10 Women of childbearing potential and men who are sexually active and not willing/able to use medically acceptable forms of contraception.
- 5.1.11 Patients unable to provide informed consent.

Recruitment

Subjects will be recruited from investigator clinical practices and include men and women with liver cancer who will be receiving definitive doses of radiation or surgical resection. Subjects will undergo an informed consent process in accordance with GCP (see section 11 Ethical Considerations). Informed consent will be obtained prior to the performance of any screening procedures.

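### The survival, CTP-progression and post-treatment-change analyses cover two non-randomised cohorts without a cohort term, so an SC metric could look prognostic by marking the cohort

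*Combined protocol and SAP*

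**What the plan says.** Section 4.0 (General Design) sets up 40 radiotherapy patients (Cohort A) and 20 surgery patients (Cohort B). Entry to a cohort follows the planned clinical treatment, and tumour types are mixed: "Patients with a diagnosis of HCC, intrahepatic cholangiocarcinoma, or metastatic liver cancer planned to receive definitive doses of radiation or surgical resection are eligible" (Section 5.0).

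Section 2.0 says that impaired liver function in cirrhosis "plays a central role in determining which treatments patients can safely receive and how aggressive these treatments can be".

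Primary objective (a) in Section 3.1 concerns "clinical outcomes in liver cancer patients receiving RT or surgery", with both treatments taken together. Its hypothesis is that global SC metrics predict survival better than conventional clinical measures do.

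For the analysis, Section 4.2.1(a) states "Imaging and clinical parameters of liver function will be tested for association with overall survival" and then "Univariate Cox proportional hazard regression will then be performed on all continuous and categorical variables". Significant variables go on to a multivariate Cox model with backward selection. The following paragraph adds toxicity, meaning CTP score progression, as an outcome. Part (b) repeats the whole set of analyses for post-treatment changes in SC uptake.

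Cohort is not named as a covariate, a stratum or a basis for separate analysis in any of these. The only cohort-specific work is dose metrics and dose-response (radiotherapy) and future liver remnant, liver failure and hypertrophy (surgery).

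**The concern.** A variable confounds the SC–survival association if it is related to both. Cohort may well be. Section 2.0 links liver function to the treatments a patient can have, so mean SC uptake may differ between cohorts. Treatment and tumour type may both affect survival. Without a cohort term, a survival gap between the cohorts would be credited to the imaging metric, and the primary hypothesis of (a) rests on that association.

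Part (b) has a second problem. By Section 4.0, the first follow-up scan is mid-radiotherapy in Cohort A and 3–5 days after resection in Cohort B, where part of the liver has been removed between scans. Section 3.1(b) itself expects different patterns: changes that track toxicity under radiotherapy, and stable uptake in the remnant after surgery. A relative change does not mean the same thing in the two cohorts, so an association estimated across both has no clear interpretation.

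**Working it through.** **The plan's own figure.** 40 + 20 = 60 adds up. No alpha, power, effect size or event count is stated, so there is no error rate or sample-size calculation to reproduce. Two-sided 0.05 is assumed below.

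**Inputs from the documents**
- Cohort sizes 40 and 20 (Section 4.0).
- Five-year survival after resection 50–70% (Section 2.0). No survival figure is given for radiotherapy.
- Record review at 6 months after treatment (Section 7.0). For patients who withdraw, survival is also sought only up to 6 months.

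**Inputs assumed**
- SC lower in radiotherapy patients by d = 0.5 or 1 within-cohort SD.
- Death hazard ratio (HR), radiotherapy versus surgery, of 2 or 3.
- Follow-up to 24 months as an alternative to 6.

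**Expected deaths.** With exponential survival, the surgical hazard is h = −ln(S5)/60 per month, and deaths by month m are 40(1 − e^(−h·HR·m)) + 20(1 − e^(−h·m)). At S5 = 50%, h = 0.0116.
- Surgical deaths by 6 months: 20(1 − e^(−0.0693)) = 1.3. At S5 = 70% the figure is 0.7.
- All deaths by 6 months, HR 2–3: 3.5 to 8.8.
- All deaths by 24 months, HR 2–3: 12.6 to 27.4.

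**Size of the spurious effect.** With p = 2/3 of patients in radiotherapy, p(1 − p) = 0.222. The approximate log HR per 1-SD drop in SC, when SC has no effect within either cohort, is ln(HR) × 0.222d/(1 + 0.222d²).
- HR 2, d = 0.5: 0.693 × 0.111/1.056 = 0.073, a spurious HR of 1.08.
- HR 3, d = 1: 1.099 × 0.222/1.222 = 0.200, a spurious HR of 1.22.

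**Type I error.** Cox score test on continuous SC with no within-cohort effect, 4,000 simulated trials per cell, S5 = 50%. The Monte Carlo standard error at 5% is √(0.05 × 0.95/4000) = 0.34 percentage points.

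| Follow-up | HR | d | Pooled | Stratified by cohort |
|---|---|---|---|---|
| 6 months | 2 | 0.5 | 5.1% | 5.1% |
| 6 months | 2 | 1 | 5.6% | 5.1% |
| 6 months | 3 | 0.5 | 6.1% | 5.6% |
| 6 months | 3 | 1 | 7.5% | 5.5% |
| 24 months | 2 | 0.5 | 6.1% | 4.9% |
| 24 months | 2 | 1 | 8.2% | 5.7% |
| 24 months | 3 | 0.5 | 8.6% | 5.3% |
| 24 months | 3 | 1 | 17.1% | 5.7% |

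Over the full 50–70% survival range the pooled rate is about 5–8% at 6 months and 5–17% at 24 months. With HR = 1 or d = 0 there is no systematic inflation (pooled 4.9–6.4% over 6 to 48 months), so both differences are needed.

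**Cost of stratifying.** Variance inflation is 1 + 0.222d². It is 1.056 at d = 0.5 and 1.222 at d = 1, so the information lost is 1 − 1/1.056 = 5% and 1 − 1/1.222 = 18%.

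**The case against.** - **Allocation.** A reader might infer that liver function decides between radiotherapy and surgery. Section 2.0 says only that it plays a central role in which treatments are safe, and gives no rule for choosing between the two. It adds that poor function can deny a patient either one. The size and direction of any SC difference between cohorts are therefore assumptions. This stands.
- **Baseline CTP comparison.** A reader might extend the point to the rank-sum and Spearman analyses of baseline SC against concurrent CTP. That does not follow. In that cross-sectional comparison cohort is largely a consequence of liver function, and adjusting for a consequence does not remove confounding and can distort the association.
- **Cut-points.** Section 4.2.1 dichotomises continuous variables at a ROC-chosen threshold. Under one reading of that step (a Youden cut on death status), simulated type I error was 27–34% with no cohort difference and 22–35% even with stratification. This is a larger source of error than cohort and needs its own remedy.
- **Adjustment already present.** CTP, ALBI, bilirubin and albumin can enter the multivariate model and may absorb part of a cohort difference. They enter only if univariately significant, and they do not encode treatment or tumour type. The wording about all continuous and categorical variables could be stretched to admit cohort, but the sentences before it concern imaging and clinical liver-function parameters.
- **Comparative hypothesis.** The hypothesis sets SC against clinical measures that share the same pooling. The effect on that comparison was not computed.
- **Tumour type.** A cohort stratum does not fully deal with it. This stands too, but so few deaths leave little room for more covariates.

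**Conclusion.** The omission is real and the mechanism works, but its size is modest and conditional. At the only record review the documents schedule, 6 months, the pooled type I error is about 5–8%, close to nominal. At an assumed 24 months it is about 5–17%, and the top requires d = 1, HR = 3 and 50% five-year surgical survival together. Stratified, it is about 5%. All these figures are for a continuous metric and leave out the cut-point step.

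A reader might infer a rate near one in four. The documents do not support that as a headline. One route is a surgical hazard of 0.2 per year, which implies five-year survival of e^(−1) = 37%, below the quoted 50–70%. The other is 48 months of follow-up, where d = 1 and HR = 3 give 25.9%, but no such follow-up is scheduled.

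The point applies to survival, CTP progression and part (b), not to the baseline SC-versus-CTP analyses. For part (b), the difference in scan timing and in what happens to the liver between scans is reason enough to separate the cohorts, whatever the assumed HR.

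**What to change.** Amend Section 4.2.1 as follows.

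1. Stratify every Cox model and log-rank test for overall survival by cohort.
2. Include cohort as a factor in the CTP-progression and toxicity models, kept in regardless of significance and exempt from backward selection.
3. Analyse the part (b) post-treatment changes separately in Cohort A and Cohort B.
4. Leave the baseline SC-versus-CTP rank-sum and Spearman analyses unadjusted.
5. Give cohort-specific survival estimates descriptively only, since about 1 surgical death is expected by 6 months.

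This needs wording only; cohort is known for every patient. The price is about 5% of the information on the SC coefficient if the cohorts differ by 0.5 SD in SC, and 18% if they differ by 1 SD. Part (b) also falls to 40 and 20 patients per analysis, so the surgical results there will be imprecise. The change does not correct the ROC-chosen cut-points, which have to be handled separately.

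### Continuous variables are to be cut at an ROC-optimised value before the survival tests, with no named ROC outcome, no single criterion and no correction; on the natural reading this inflates false positives for every marker so cut

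*Combined protocol and SAP*

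**What the plan says.** Section 3.1(a) makes it a primary hypothesis that global baseline SC metrics "are more predictive for survival than conventional clinical measures of liver function". Section 4.2.1(a) gives the analysis in consecutive sentences:

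- The first says that both kinds of measure, from the scans and from the clinic, are to be examined for a link with survival.
- The second sets the cut: "Continuous variables will be dichotomized above and below a threshold value that maximized accuracy of classification under ROC with balanced sensitivity and specificity".
- The third describes the modelling step, which is placed after the cut: "Univariate Cox proportional hazard regression will then be performed on all continuous and categorical variables".
- The fourth passes whichever variables reach significance to the multivariable Cox model. Backward elimination follows.

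The clinical measures listed in that section are the numeric CTP score, ALBI grade, albumin, bilirubin, INR and several yes/no signs. Item (b) applies the same set of analyses to post-treatment changes. Section 4.0 sets enrolment at 60 (40 in Cohort A, 20 in Cohort B).

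Two other places mention ROC. The synopsis in section 1.0 uses it to classify liver function, and section 4.1.1(a) uses it to choose image thresholds against CTP class A versus B/C. Neither concerns survival. The synopsis ties cross-validation to the prediction models in the machine-learning framework. Section 4.2.1 contrasts that framework with standard methods, Cox among them. No significance level, cut-point correction or hold-out sample is given for the dichotomisation.

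**The concern.** A cut chosen because it best separates the patients who died from those who did not, and then tested against survival in those same patients, does not have its nominal error rate. The chosen split is the best of many, but the test treats it as the only one. False positives then pass the univariate screen into the multivariable model. Because of item (b), this affects both primary objectives.

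The sentence also leaves three choices open to the analyst: the ROC outcome, the criterion, and whether the cut or the continuous variable enters Cox. What is at stake is whether a reported survival association, for an SC metric or a clinical measure, can be taken at face value.

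**Working it through.** The plan states no alpha, power, effect size or event count, so there is no figure to reproduce.

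**Inputs.** From the plan: N = 60. Assumed: two-sided alpha 0.05; deaths in 10-70% of patients (6 to 42 of 60); exponential survival with uniform censoring; a fixed class with about 30% of patients in the worse group, as a stand-in for CTP class.

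**The criteria differ.** Let d be the proportion who die.

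- Accuracy = d × sensitivity + (1 − d) × specificity.
- Youden: maximise sensitivity + specificity − 1. Balanced accuracy, (sensitivity + specificity)/2, gives the same cut.
- Closest to corner: minimise (1 − sensitivity)² + (1 − specificity)².
- Strict equality: sensitivity = specificity.

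With 15% deaths (9 of 60), calling everyone a survivor is right in 51/60 = 85% of patients, with zero sensitivity. At a cut where sensitivity = specificity = s, accuracy is d·s + (1 − d)·s = s. That cut has the higher accuracy only if s exceeds 85%. Highest accuracy and balance can therefore point to very different cuts.

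**False-positive rate.** One marker unrelated to survival was cut on death status and tested by log-rank, which is the Cox score test for a binary covariate. N = 60; 4,000 trials per row for 10-20% deaths and 6,000 for 30-70%. Simulation error is about ±1.5 percentage points at most.

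| Deaths (assumed) | Youden | Corner | Strict equality | Cut trained on CTP class | Kept continuous |
|---|---|---|---|---|---|
| 10% | 33.9% | 26.5% | 8.2% | 4.2% | 5.1% |
| 15% | 32.5% | 22.9% | 6.7% | 4.4% | 5.3% |
| 20% | 33.9% | 22.1% | 6.3% | 4.9% | 5.8% |
| 30% | 33.5% | 19.9% | 5.4% | 4.8% | 5.2% |
| 50% | 32.7% | 19.0% | 5.5% | 5.1% | 5.6% |
| 70% | 28.1% | 17.0% | 5.4% | 5.3% | 5.8% |

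A repeat with administrative censoring and 15-50% deaths gave 33-35% (Youden), 20-23% (corner) and 5-6% (strict equality). Relative to the nominal 5%, the first two rules inflate error by 17/5 = 3.4 to 35/5 = 7 times.

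**Does SC gain over clinical measures?** N = 60, 50% deaths, 3,000 trials, both markers uninformative. The table shows how often SC has the larger test statistic (50% is neutral).

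| SC cut | Against a fixed class | Against a continuous clinical marker that is also cut |
|---|---|---|
| Youden | 84% | 49% |
| Corner | 76% | 51% |
| Strict equality | 52% | 51% |

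With equally informative markers, SC's share against the fixed class is 73-77% (Youden) and 65-67% (corner). Against the cut clinical marker it stays at 49-51%. An SC cut trained on CTP class gives 46-49% against the fixed class.

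**Cost when error is not inflated.** With 25% deaths (15 of 60), the strict-equality cut has 32% power against 44% for the continuous term at a hazard ratio of 1.6 per SD, and 55% against 73% at 2.0. A median split, used here as an example of a cut not fitted to survival, gives 30% against 45% and 53% against 77%.

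**The case against.** The strongest reply is that the plan may not do what is feared:

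- Wherever the documents name an ROC outcome, it is liver function, not survival. A cut trained on CTP class leaves the false-positive rate at 4-5%.
- The sentence asks for balance, and strict balance gives only about 5-8%. The same words rule out an extreme maximum-accuracy cut that isolates one or two patients.
- Cox is to be run on continuous as well as categorical variables, so the cuts may serve only the Kaplan-Meier and log-rank analyses in the synopsis.
- This is a single-arm pilot with no stated alpha or success criterion.

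Each of these limits the size of the problem, and the last bears on severity. None removes it. The dichotomisation stands between a sentence about overall survival and one saying Cox will then be run, so survival is the natural target and the cut form the natural input. Youden is also a fair reading of accuracy with balance, because balanced accuracy selects the same cut. If the cuts serve only log-rank tests, those tests are inflated in the same way.

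A reader might infer that SC metrics alone receive a fitted cut and that the comparison with clinical measures is tilted towards SC throughout. The documents do not support that. The rule covers every continuous variable, so albumin, bilirubin and INR are cut as well, and the numeric CTP score could be. Only ALBI grade, CTP class (if used) and the yes/no signs escape.

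**Conclusion.** The concern holds in a conditional form. If the cut is fitted to survival, the false-positive rate for one uninformative marker rises from 5% to about 28-35% (Youden) or 17-27% (closest to corner), but only to about 5-8% under strict equality. The inflation applies to any continuous marker, imaging or clinical. SC is favoured only over fixed-category measures, and only under the first two rules. If the cut is trained on CTP class, error is not inflated, but information is still lost.

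These figures rest on assumed deaths of 10-70%, an assumed two-sided alpha of 0.05, an assumed 30% share in the worse fixed class, and simulated survival times. It would go too far to say that a third of null findings will be declared significant, because the plan does not fix the target, the criterion or the form entering Cox. Severity: should-fix for a pilot.

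**What to change.** Delete the dichotomisation from the survival tests in section 4.2.1(a), and so from item (b). Enter SC metrics, albumin, bilirubin, INR and CTP score in Cox as continuous standardised terms. The simulated false-positive rate is then about 5-6%. Compare SC with the clinical measures on one scale, such as an optimism-corrected C-index.

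For Kaplan-Meier plots, use the median or another cut fixed beforehand. If an ROC cut is kept for description, name its outcome and its single criterion. Attach no p-value to a cut chosen in these data. State the significance level and the expected number of deaths as assumptions.

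The change is to wording only and needs no extra patients or procedures. The cost is that hazard ratios are per SD rather than high versus low, and some p-values become less favourable.
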